The second study is a randomized control trial of YLWH initiating ART to determine the effect of the CFLU mHealth tool on ART adherence. A total of 206 YLWH will be randomized to either Standard of Care (SoC) or CFLU plus SoC. Through the CFLU mHealth tool, participants will interact with a computer through IVR. Participants in the intervention arm will receive pill reminders, clinic visit reminders, health tips messages and functionality to support self-reported symptoms in addition to standard of care. During this second part of the research, youths will be assessed on knowledge of COVID-19 at baseline only.

The third study is nested within the randomized control trial and will assess the cost of the CFLU intervention when compared to SoC.

Conclusion

This project will determine acceptability, effectiveness, knowledge of COVID-19 and cost of delivering pill and clinic visit reminders, and messages on health tips to a population with suboptimal ART adherence. Results from this research will provide valuable insights into mHealth adherence interventions for YLWH and knowledge of COVID-19 in resource-limited settings.

CHAPTER ONE: INTRODUCTION

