Many people newly diagnosed with HIV are lost to follow-up shortly before or after timely initiation of antiretroviral therapy. One study in Kenya documented that people living with HIV

felt that increased communication via the text messaging intervention had the potential to enable early identification of problems, leading to timely problem solving that could improve retention and engagement in care during the first year after diagnosis. Engaging PLWH at all points along the cascade of care is essential for transforming the management of the disease from a fatal condition to a chronic one (Edward M. Gardner, McLees, Steiner, Del Rio, & Burman, 2011; Smillie et al., 2014).

[figure not shown]
In a recently published community-based individual randomized trial in Uganda, no statistically significant differences in retention were observed in the first 6 months between those randomized to either mobile-phone or physical contact tracing reminders. Retention was higher among those who received physical contact reminders at month 12 (91.5% versus 82.1%; p=X) (Kiwanuka et al., 2018). Although physical contact tracing reminders had higher retention at 12 and 18 months, mobile technology has several advantages which may be cost saving. The challenges of physical contact included structural barriers, time consuming, health care worker exhaustion and physical infrastructure challenges.

Various studies in Uganda have shown that patient-related factors resulting in loss to follow-up include transportation costs, distance to health centers, inconsistent income and lack of social support. Financing of transport improved retention, but this option is not cost effective nor sustainable in resource poor countries (Emenyonu et al., 2010; Kasigeire, 2014; Tuller et al., 2010).

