The tool capitalises on a basic mobile phone's core utilities of voice and short messaging services. The system design, development, testing and evaluation was done by Janssen and the Grameen Foundation (<http://motechsuite.org/index.php/implementations>). In 2015, Janssen Global Public Health Research and Development, in close collaboration with the Infectious Diseases Institute Kampala (IDI), developed Call for Life Uganda (CFLU) tailored to the needs of PLHIV in Uganda. The CFLU system follows the Health Insurance Portability and Accountability Act (HIPAA) Privacy and Security rules. While the Privacy rules deals with electronic Protected Health Information, the security rule covers administrative, physical and technical safeguards to ensure confidentiality, integrity and security of electronic protected health information. Data transaction between patient and system is encrypted when it comes to human subjects. The system is password protected, and interaction of system and patient is personalised with a secret code. The system interacts with the patient through a basic mobile phone via a keypad and with the health worker through a web-based interface. The system has options to either use interactive voice response or short message service and the user has to make a choice, get a secret pin code which ensures privacy to enduser.

Screening-Enrolment procedures:

All potential participants will be written on the screening log, and a screening form completed, reasons for screen failure will be documented on the screening log. Following successful screening, the participant will be referred to the Research Assistant (RA) to receive a

thorough explanation of the study so and informed consent is obtained. The RA then administers the stigma questionnaire along with the sociodemographic and medical information, , HIV knowledge and sexual behaviour questionnaires. A client locator form will be completed which will help in physical contact tracing, and the participant will be registered on the enrolment log.

Randomisation will follow (see details of randomisation procedure below) thereafter and the result in the sealed envelope will dictate whether the patient will be registered onto the Call for Life System for the intervention or continue with standard of care as per MoH HIV Management guidelines.

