The Adult Care and Treatment Package includes the following services:(U. MoH, September 2014)

1. HIV counseling and testing
2. HIV prevention services
3. Nutritional Counseling and support
4. Opportunistic infection screening and management
5. Screening and management of non-communicable diseases
6. Diagnostics and laboratory monitoring
7. Sexual and reproductive health
8. Counseling and Psychosocial support
9. ARV preparation, initiation and monitoring
10. Adherence and retention into care
11. Palliative care
12. Mental health

[figure not shown]
[figure not shown]

Fig 5: Study Schema

The outcome variables include:

- ART adherence scores at 6 and 12 months, as assessed by HIV Care Card for those on SoC arm and Self- reported adherence to ART as depicted on the mHealth dash board.
- Viral load suppression at 6 and 12 months, as test results from blood collected at months 6 and 12 with time to viral suppression.
- Retention rates at 6 and 12 months with time to loss to follow-up
- Stigma scores at study start and end

Data Management Analysis Plan

Data collected on paper CRF will be entered using Research Electronic Data Capture software (REDCap) which is a safe, secure, HIPAA-compliant, web-based application and facilitates offline and online data entry. Data will be exported to STATA 14.0, for analysis. Data will then be backed up and archived in both soft and hard copy to avoid losses. The data collected will be stored securely under lock and key to maintain patient confidentiality.

Data regarding call details in the system will be extracted from CFL tool database, exported into Stata for analysis.

[figure not shown]
Visit dates will be extracted from database and proportions lost to follow-up drawn and time to loss to follow-up estimated. Viral load results will be extracted and time to viral suppression with survival analysis curves drawn for both arms.

Data from the MoH HIV card regarding the ART regimen and start dates will be transcribed to the data collection tool and later entered on the REDCap system.

General data analysis

Data will be analyzed at three levels, first at the univariate level, then at the bivariate level and lastly at the multivariate level. A consort diagram will be drawn to show the screening, enrolment, randomization, follow-up and analysis flow of the study.

Univariate Analysis

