During enrolment, it is important to obtain the names and contact information for several individuals closely related to the participant (e.g., next of kin, friends, etc.). Such individuals can be contacted in the event that a participant does not return for follow-up visits. Physical contact tracing will happen if the patient takes 2 weeks past the scheduled visit.

Missed visit:

When the appointment is not honoured and the 14-day window passes, this is a missed visit. If a participant misses a visit (Visit window inclusive) a missed visit form is completed documenting the reason for missing (if known) and the attempts made to contact the participant, through mobile

phone or physical tracing. Several attempts to contact the participants must be made to ensure good retention. The attempts may include: Checking the General clinic schedule to sync the appointment visit, Calling the participant; Calling a relative who was disclosed to, or Visiting the participant's home: To minimise missed visits, through the web-interface on CFLU system, any dropped calls monitored on the dashboard, will trigger active follow-up and tracing of the participants.

Loss to follow-up:

If a participant misses 2 consecutive visits and unable to ascertain the vital status, this patient will be declared lost to follow-up, alternatively, if 3 months consecutively elapse, without acknowledging the patient's status, the patient will be labelled lost to follow-up. If a participant's whereabouts are not known for 3 months and the contact tracing is uneventful after 3 documented attempts, this participant is deemed lost to follow-up and a withdraw form is completed. In case the participant re-surfaces to the clinic when the study is still active/ongoing, the withdraw form is cancelled out and patient re-joins the study and a study visit is conducted.

Study Objective 3:

To evaluate the cost of mHealth in comparison to Standard of Care

Study design: Cost evaluation analysis

Study Purpose: To assess cost of mHealth intervention in comparison to standard of care

[figure not shown]
Primary outcome measure: Costs spent on the intervention participants in comparison to standard of care participants

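### Dropped CFLU calls trigger tracing in one arm only, so loss to follow-up is ascertained differently by arm and a retention difference belongs to CFLU plus triggered tracing

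*Combined protocol and SAP*

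**What the plan says.** Section 3.4, Study Objective 2, Missed visit: to keep missed visits down, "any dropped calls monitored on the dashboard, will trigger active follow-up and tracing of the participants". Under Screening-Enrolment procedures, the randomisation envelope decides "whether the patient will be registered onto the Call for Life System for the intervention or continue with standard of care", and Section 3.5 likewise registers only those randomised to CFLU.

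The other tracing provisions carry no arm restriction. Before randomisation, "A client locator form will be completed which will help in physical contact tracing". Under Study visits, "Physical contact tracing will happen if the patient takes 2 weeks past the scheduled visit". After a missed visit, the attempts may include calls to the participant or a relative and a home visit.

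The outcome list includes "Retention rates at 6 and 12 months with time to loss to follow-up". Under Loss to follow-up, a participant can be declared lost in two ways: two consecutive missed visits with vital status not ascertained, or three months without known status. A further sentence ties the three-month route to three documented attempts. Follow-up visits fall at days 168 and 336, each with a 14-day window either side.

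On content, the Abstract states: "Participants in the intervention arm will receive pill reminders, clinic visit reminders, health tips messages and functionality to support self-reported symptoms". Study Objective 2 gives a similar list. Neither mentions tracing.

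**The concern.** An early prompt to look for a participant exists in one arm only, and it acts on a listed outcome in two ways. It may bring people back who would otherwise have dropped out. It also supplies information on status, and information on status is what part of the loss definition turns on. A between-arm difference in retention or time to loss would then mix three things: the effect of the automated calls, the effect of the tracing they set off, and a difference in how loss is detected.

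The plan could not separate these afterwards. Contact attempts are recorded on the missed visit form, which is completed only once a visit has been missed. No record is described for contacts set off by the dashboard, and the Objective 3 cost list has no tracing item. A programme that adopted the calls without the tracing would not know whether to expect the same retention.

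**Working it through.** **1. Triggers side by side**

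| Trigger | CFLU | SoC |
|---|---|---|
| Scheduled visit overdue by 2 weeks | yes | yes |
| Whereabouts unknown for 3 months | yes | yes |
| Dropped call on the dashboard | yes | cannot arise |

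**2. Calendar of the loss definition**

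Inputs: visits at days 168 and 336, window ±14 days (Study visits). Assumption: 3 months = 91 days.

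- The month 6 window closes at 168 + 14 = day 182, the first point at which the visit rule starts tracing.
- A participant last seen at baseline passes 3 months at day 91, which is 182 − 91 = 91 days earlier.
- A participant last seen at day 168 passes 3 months at 168 + 91 = day 259. The next visit-based trigger is at 336 + 14 = day 350, again 91 days later.
- There are only two scheduled follow-up visits, so two consecutive missed visits can be established only at day 350. Before then, the contact-based route is the only one that can date a loss.

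In CFLU, daily calls and the follow-up of dropped ones yield information throughout these gaps. In SoC the plan provides no such source. Two participants who behave alike can therefore be classified or dated differently. The direction is not fixed: a contact may prevent a label of loss, while failed early attempts may bring the date of loss forward. Routine clinic contact could narrow the gap in both arms, but the plan does not say whether it counts.

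**3. Illustration of size**

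The plan gives no figure for this comparison. Its arm size reproduces from its own 93 per arm: 93 × 1.10 = 102.3, rounded up to 103. That calculation rests on viral suppression and is not affected by this point.

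Inputs: SoC retention R = 79% (site figure, Study Objective 2 and Table 1) or 90% (the plan's 10% loss allowance); n = 103 per arm; no effect of the calls. Assumption: triggered tracing keeps a share s of those otherwise lost.

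Apparent gain = (1 − R) × s. The chance of significance uses the two-sided 5% normal test of two proportions:

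Φ{ [d√n − 1.96√(2p̄(1 − p̄))] / √(p₁(1 − p₁) + p₂(1 − p₂)) }, where p₂ = R, p₁ = R + d, d is the gain and p̄ is the mean of p₁ and p₂.

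For R = 0.79 and s = 0.25: d = 0.21 × 0.25 = 0.0525, p₁ = 0.8425, p̄ = 0.81625. The argument is (0.533 − 1.073)/0.546 = −0.99, giving about 16%.

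| s | Gain, R = 79% | Chance of p < 0.05 | Gain, R = 90% | Chance of p < 0.05 |
|---|---|---|---|---|
| 10% | 2.1 points | 6% | 1.0 point | 4% |
| 25% | 5.3 points | 16% | 2.5 points | 9% |
| 50% | 10.5 points | 54% | 5.0 points | 27% |
| 75% | 15.8 points | 92% | 7.5 points | 61% |

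The share s is not known from the documents, so the table shows sensitivity and is not an estimate.

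**The case against.** The strongest reply is that the tracing belongs to what is being tested. Section 1.1 presents near-real-time data, and the ability of investigators to step in when a participant has a problem, as a feature of the tool. The hypothesis in Section 1.2 joins early follow-up of missed appointments to adherence support. The dashboard trigger itself runs through the CFLU web interface. On that reading, CFLU plus SoC against SoC is a sound randomised package comparison. This stands. A reader might infer that the trial compares tracing intensities instead of CFLU, and the documents do not support that. What remains is that the intervention descriptions omit tracing, Section 1.2 speaks of missed appointments and not dropped calls, and the trigger sits among the missed-visit procedures. The protocol never says whether it is intervention or study conduct.

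Three other stronger readings also fail.

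- **Borrowing a size from the trial cited in Section 2.4.** That trial found 91.5% against 82.1% retention at month 12, but it compared physical-contact with mobile-phone reminders as alternatives. Here both arms are traced after a missed visit and the difference is an earlier prompt in one. The same paragraph reports no significant difference in the first 6 months.
- **Counting daily calls against scheduled visits as a measure of imbalance.** That counts opportunities, not traces. A dropped call has no definition or threshold, and the text does not say who traces or that a home visit follows.
- **Concluding that viral load results will be missing unequally by arm.** Blood is drawn at the month 6 and 12 visits, so this could happen, but nothing in the documents shows that it will or by how much.

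It is also fair that the plan takes proportions lost from visit dates. That limits the labelling problem without removing it, because the written definition of loss still turns on contact.

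**Conclusion.** The point holds as a gap in specification. Following the plan as written, loss and time to loss are ascertained differently in the two arms, and a retention difference is the effect of CFLU plus triggered tracing, not of the automated calls alone. The package comparison itself remains valid.

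The real size cannot be computed. Under the stated assumptions (no effect of the calls, 103 per arm, and 25% to 50% of would-be losses kept by tracing), the apparent gain is 5.3 to 10.5 points at 79% SoC retention and 2.5 to 5.0 points at 90%. The conclusion about ascertainment does not depend on those figures. It follows from a one-arm trigger, a contact-based definition and visits 168 days apart.

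**What to change.** 1. In the outcome list and the Missed visit and Loss to follow-up text of Section 3.4, define retention and loss for the between-arm comparison by one rule applied identically in both arms. Use attendance within the month 6 and month 12 windows and, after a missed window, the same number and type of tracing attempts. Do not use dashboard call data or dashboard-triggered contacts to classify a loss or to date it. Locator forms taken before randomisation and phones given to everyone make this feasible.
2. Keep the dashboard-triggered follow-up. Name it as a CFLU component in the Abstract and in Study Objective 2, log each contact by date, type and trigger, include it in the Objective 3 costs, and word the retention conclusion as the effect of CFLU plus triggered tracing.

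The first change equalises ascertainment. It does not remove any effect of tracing on attendance, which is why the second is also needed. The cost is protocol wording, modest logging time and a narrower conclusion. No planned outreach is withdrawn and the sample size does not change.

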Loss to follow-up: Missing 2 visits consecutively, not able to ascertain vitals

mHealth: use of mobile technology e.g. mobile phones and other wireless technology for health-related activities

Retention in care: Continuous engagement in clinical care for 1 year

Virological suppression: Viral load less than 1000 copies/ml

Youth Living with HIV/AIDS: Persons living with human immunodeficiency virus/ acquired immunodeficiency syndrome aged 15 to 24yrs (United Nations General Assembly Resolution A/RES/50/81 ("World Programme of Action for Youth to the Year 2000 and Beyond"))

LIST OF ABBREVIATIONS

AIDS: Acquired Immuno Deficiency Syndrome

cART: Combined Antiretroviral Therapy

CD4 cell: Cluster Differentiated cells

cDOT: Community based Directly Observed Treatment

CFLU: Call for Life Uganda

CITI: Collaborative Institutional Training Initiative

COVID-19: CORONA VIRUS DISEASE 2019

GCP: Good Clinical Practice

HIT: Health Information Technology

[figure not shown]
HIV RNA: Human Immunodeficiency Virus Ribonucleic Acid

HSP: Human Subjects Protection

IAC: Intensive Adherence Counselling

IDI: Infectious Diseases Institute

IVR: Interactive Voice Response

MoH: Ministry of Health

PEPFAR: President's Emergency Plan for AIDS Relief

PHS: Physical Health Scores

PLWH: People living with HIV

SMS: Short Messaging Service

[figure not shown]
UBOS: Uganda Bureau of Statistics

UNAIDS: United Nations Programme on HIV and AIDS

UPHIA: Uganda Population-Based HIV Impact Assessment

VL: Viral load

YLWH: Youth living with HIV

ABSTRACT

Version 3.2, 12th Jan 2022

Background:

An estimated 3.9 million[2.1–5.7 million] youth were living with HIV (YLWH) globally in 2017, most of whom live in sub-Saharan Africa (Avert.Org, 2019; UNAIDS, 2018b). Young people are the only population group in which AIDS-related deaths are increasing (UNAIDS, 2019a). AIDS is the leading cause of death among young people in sub-Saharan Africa (Avert.Org, 2019).

In Uganda, there were 160,000 YLWH in 2018 (UNAIDS, 2019b). An estimated 53,000 new HIV infections occurred among youth in 2018, accounting for 26% of HIV incidence in the country (Avert.Org, 2019).

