2.6 Hypotheses and Research Questions

[figure not shown]
1. What is the acceptability of mHealth among YLWH at three (03) of Kiryandongo District HIV Centres, and what are the barriers, facilitators/enablers of ART and clinic visit adherence?

Hypothesis: YLWH will have a high acceptability for mHealth with 70% accepting to use mHealth.

2. What is the effect of the mHealth-CFLU tool on ART adherence among YLWH?

Hypothesis: More than 79% of YLWH using the mHealth-CFLU tool will be adherent to ART (using viral load suppression as a proxy measure for ART adherence we anticipate an increment of 15%).

3. What is the cost of the mHealth CFLU intervention compared to standard of care over a 12 month period?

Hypothesis: mHealth will be cost effective by increasing proportion in care and proportion with viral suppression compared to standard of care

CHAPTER THREE: METHODS

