A cost analysis of the intervention from a governmental perspective will be performed. The principle of marginal costing will be used to cost the resources utilised in the alternative strategies. All costs of a historical nature, the sunk costs such as resources invested in buildings, equipment, and vehicles will be ignored. Only costs related to the future, from the onset of the study, will be recorded.

[figure not shown]
Sources of cost information: The following costs will be assessed and classified under direct or indirect cost: Sources of cost data will be; program/ project documents, financial records.

Capital costs:

I. System Costs:

- Software monthly hosting (internet, cloud hosting, call bills,)
- Support maintenance
- Hard ware
 - Computers
 - Internet modem

Recurrent costs:

- I. Supplies (blood collection tubes, vacutainer holders, needle, cotton swabs)
- II. Transport to fro (clinic visit):
- III. Staff/ personnel salaries:

Induced costs:

- I. Transport costs
- II. Number of sick visits attended outside the clinic costs/fees incurred
- III. Airtime fees

Health outcomes:

The number of patients with viral suppression (<1000 copies) will listed per study arm at month 6 and 12, and these will be compared across arms.

Analysis:

Primary outcome measure will be Cost for mHealth Intervention.

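### Hypothesis 3 predicts that CFLU will be cost effective, but the plan only compares costs, so it cannot judge the plausible result of higher cost with better outcomes

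*Combined protocol and SAP*

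**What the plan says.** Hypothesis 3 in section 2.6 reads: "mHealth will be cost effective by increasing proportion in care and proportion with viral suppression compared to standard of care". The research question directly above it is narrower: "What is the cost of the mHealth CFLU intervention compared to standard of care over a 12 month period". Specific objective IV in section 1.3.2 also asks only for cost against standard of care (SoC), at 12 months.

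Study Objective 3 in section 3.4 is designed as a cost evaluation from a governmental perspective. Its outcome is first given as "Primary outcome measure: Costs spent on the intervention participants in comparison to standard of care participants". Under its health outcomes it states: "The number of patients with viral suppression (<1000 copies) will listed per study arm at month 6 and 12", and adds that these counts will be compared between arms. The analysis paragraph is one sentence: "Primary outcome measure will be Cost for mHealth Intervention".

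Retention appears in the outcome list for Study Objective 2: "Retention rates at 6 and 12 months with time to loss to follow-up". Item IV of the list of possible manuscripts (section 5) pairs cost with retention in a title and gives no method.

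**The concern.** A claim of cost effectiveness relates a difference in cost to a difference in outcome and judges the result against a criterion. Hypothesis 3 makes such a claim and names two outcomes. The planned analysis yields a cost comparison and, separately, a suppression comparison. It has no step that combines them, and no rule for how much extra cost per additional suppressed or retained youth would be acceptable.

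If the criterion is left until the cost data have been seen, the result can choose the criterion. Section 2.5 reports that missing cost-effectiveness evidence hampers mHealth implementation, so readers are likely to give weight to this claim.

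**Working it through.** **1. What the planned outputs can settle.** Let ΔC be the cost per participant under CFLU minus SoC, and ΔE the difference in the proportion suppressed (or retained).

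- ΔC ≤ 0 and ΔE ≥ 0, not both zero: CFLU dominates. The separate comparisons are enough to support the hypothesis.
- ΔC ≥ 0 and ΔE ≤ 0, not both zero: SoC dominates. The same outputs count against the hypothesis.
- ΔC > 0 and ΔE > 0: undecided without a ratio ΔC/ΔE and a threshold W.
- ΔC < 0 and ΔE < 0: the economic verdict again needs a threshold, although the benefit that the hypothesis predicts would be absent.

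With two outcomes, a dominance verdict also requires suppression and retention not to point in opposite directions.

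**2. Which case is plausible.** The Abstract describes the arms as SoC and CFLU plus SoC. Both arms receive a basic phone (section 3.4), so that item cancels. The CFLU arm adds hosting, call bills and support maintenance, all listed under Objective 3. Unless savings elsewhere offset these, ΔC is positive. The trial is powered on a positive ΔE. The third case is therefore a natural expectation.

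**3. The planned effect, reproduced.** Inputs from the sample size section: 79% against 94%, two-sided 5% level, 80% power, 1:1 allocation.

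- Fleiss: (1.96·√(2·0.865·0.135) + 0.842·√(0.94·0.06 + 0.79·0.21))² / 0.15² = 80.3. The plan prints 80.
- With continuity correction: (80.3/4)·(1 + √(1 + 4/(80.3·0.15)))² = 93.1. The plan prints 93.
- 93 × 1.10 = 102.3, rounded up to 103 per arm, or 206 in total, as stated.

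The sample size reproduces apart from rounding, and the 15-point effect can serve as an illustrative denominator.

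**4. What a ratio would look like (illustration only).** With 93 analysed per arm:

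- SE = √(0.94·0.06/93 + 0.79·0.21/93) = 0.0489, so the 95% CI is 0.15 ± 1.96·0.0489, or 5.4 to 24.6 points.
- Cost per additional suppressed youth = ΔC/0.15 = 6.67·ΔC. Over the effect CI, with ΔC held fixed, it runs from ΔC/0.2458 = 4.07·ΔC to ΔC/0.0542 = 18.46·ΔC.
- Assumed ΔC of $10, $25, $50 and $100 gives $67, $167, $333 and $667 at 15 points, and $200, $500, $1,000 and $2,000 at 5 points.

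The ΔC values are assumptions, because the documents give no incremental cost per participant. At an assumed $50 and the planned effect, CFLU passes any threshold above $333 and fails any below it. The plan states none.

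**The case against.** The strongest reply is that this is simply a cost study. The abstract objective, specific objective IV, the research question, and the title, design and purpose of Objective 3 all say so. On that reading the plan is coherent and one hypothesis line is misworded. That stands, and it is why rewording is offered as a full remedy, on a par with adding an analysis.

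It can also be said that suppression is placed beside cost, and that the manuscript title shows an intention to relate cost to retention. Both are true, but neither is a method.

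Three stronger readings are tempting, and the documents do not support them.

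- A reader might infer that the plan can neither support nor refute Hypothesis 3. It can do either under dominance, from comparisons already planned.
- A reader might see a contradiction between the two statements of the primary outcome. The later one reads as shorthand for the comparison defined earlier in the same section.
- A reader might suspect that transport is counted twice, since "Transport to fro (clinic visit" is a recurrent cost and transport recurs under induced costs. The second entry sits beside sick visits made outside the clinic, so a distinction is plausible.

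One further objection shapes the fix. Objective 3 takes a governmental perspective but lists transport, outside sick-visit fees and airtime without saying who pays. A ratio built on an unsettled numerator would be of little use.

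**Conclusion.** The concern holds in this form: Hypothesis 3 claims cost effectiveness through two outcomes, while the plan specifies a cost comparison, an unlinked suppression comparison, and no criterion. *Cost effective* can be judged only where one arm is both no dearer and no worse. The plausible case in which CFLU costs more and works better is left without a rule.

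The size of the gap in money cannot be stated. The 6.67 multiplier and its range of 4.07 to 18.46 rest on the planned 79% and 94%, 93 analysed per arm and a fixed ΔC. They illustrate why a criterion is needed and do not forecast the result. The conclusion rests on the text, not on these figures. It should be corrected, but it concerns a nested objective and leaves the trial's efficacy conclusion untouched.

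**What to change.** Do one of the following.

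**(a) Add the joint analysis to Objective 3.**

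- Pre-specify the incremental cost (CFLU minus SoC) per additional youth virally suppressed at month 12 and, as secondary, per additional youth retained at month 12.
- For retention, use the Objective 2 outcome with the loss-to-follow-up rules in section 3.4. The front-matter definition, "Retention in care: Continuous engagement in clinical care for 1 year", is less suitable: continuous engagement is not made operational, and the last scheduled visit is at day 336 ± 14, so at most day 350, short of a year.
- Report the cost difference, and the effect difference with its 95% CI.
- Include only cost items that fit the governmental perspective, or state a perspective that covers items borne by participants.
- Conclude *cost effective* only under dominance, or against a threshold fixed before the cost data are analysed.

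**(b) Reword Hypothesis 3** as a cost comparison, matching its research question and objective.

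Option (a) takes a few lines and a short calculation from cost records and outcomes already planned, with no new data collection. Its price is a little more analysis, a threshold that has to be defended, and possibly a less favourable economic claim. Option (b) changes one line and gives up the cost-effectiveness claim.
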